8. LIST OF TABLES AND LISTINGS

Topline TLFs are flagged as 'TL'.

8.1 TABLES

GENERAL CHARACTERISTICS

14.1.1.1	Analysis Sets	RND	
14.1.1.2	Subject Disposition	SAF	TL
14.1.1.3	First and Last Contact in the Study	RND	
14.1.1.4	Analysis Phase Duration	SAF	
14.1.1.5	Major Protocol Deviations	SAF	
14.1.2.1	Demographic Data	SAF	TL
14.1.2.2	Vaccine Administration, Overall and by Vaccinated Cohort	SAF	
14.1.2.3	Influenza Challenge, Overall and by Challenge Cohort	SAF	
14.1.2.4	Time Between Vaccination and Challenge	SAF	

EFFICACY

14.2.1.1.1	qPCR Viral Shedding - qPCR vAUC (Primary Endpoint)	ITT	TL
14.2.1.1.2	qPCR Viral Shedding - qPCR vAUC (Primary Endpoint) - Per Protocol Set	PP	TL
14.2.1.1.3	qPCR Viral Shedding - qPCR vAUC (Primary Endpoint) - Challenge Safety Set	CSAF	TL
14.2.1.1.4	qPCR Viral Shedding - qPCR vAUC (Primary Endpoint) - Multiple Imputation	ITT	
14.2.1.1.5	qPCR Viral Shedding - qPCR vAUC (Primary Endpoint) - ANCOVA	ITT	TL
14.2.1.1.6	qPCR Viral Shedding - qPCR vAUC (Primary Endpoint) - ANCOVA - Multiple Imputation	ITT	
14.2.1.2	qPCR Viral Shedding - qPCR Attack Rate (Secondary Endpoint)	ITT	
14.2.1.3	qPCR Viral Shedding - Rate of Virologically Confirmed Influenza-like Illness (Secondary Endpoint)	ITT	
14.2.1.4	qPCR Viral Shedding - Time to Start of Viral Shedding (qPCR) (Secondary Endpoint)	ITT	
14.2.1.5	qPCR Viral Shedding - Peak Viral Shedding (qPCR) (Secondary Endpoint)	ITT	
14.2.1.6	qPCR Viral Shedding - Time to Peak of Viral Shedding (qPCR) (Secondary Endpoint)	ITT	
14.2.1.7	qPCR Viral Shedding - Time to Cessation of Viral Shedding (qPCR) (Secondary Endpoint)	ITT	
14.2.1.8	qPCR Viral Shedding - Duration of Viral Shedding (qPCR) (Secondary Endpoint)	ITT	
14.2.1.9	qPCR Viral Shedding - log qPCR Actual Values Over Time	ITT	TL
14.2.1.10	qPCR Viral Shedding - log qPCR Mixed Model for Repeated Measures	ITT	TL
14.2.2.1.1	Culture Viral Shedding - Culture vAUC (Secondary Endpoint)	ITT	
14.2.2.1.2	Culture Viral Shedding - Culture vAUC (Secondary Endpoint) - ANCOVA	ITT	
14.2.2.2	Culture Viral Shedding - Culture Attack Rate (Secondary Endpoint)	ITT	

	Statistical Analysis Plan	
	FLU010	Final analysis

14.2.2.3	Culture Viral Shedding - Time to Start of Viral Shedding (Culture) (Secondary Endpoint)	ITT	
14.2.2.4	Culture Viral Shedding - Peak Viral Shedding (Culture) (Secondary Endpoint)	ITT	
14.2.2.5	Culture Viral Shedding - Time to Peak of Viral Shedding (Culture) (Secondary Endpoint)	ITT	
14.2.2.6	Culture Viral Shedding - Time to Cessation of Viral Shedding (Culture) (Secondary Endpoint)	ITT	
14.2.2.7	Culture Viral Shedding - Duration of Viral Shedding (Culture) (Secondary Endpoint)	ITT	
14.2.2.8	Culture Viral Shedding - log Culture Actual Values Over Time	ITT	
14.2.2.9	Culture Viral Shedding - log Culture Mixed Model for Repeated Measures	ITT	
14.2.3.1.1	Influenza Symptoms - Overall SSC AUC (Secondary Endpoint)	ITT	TL
14.2.3.1.2	Influenza Symptoms - Overall SSC AUC (Secondary Endpoint) - Multiple Imputation	ITT	
14.2.3.1.3	Influenza Symptoms - Overall SSC AUC (Secondary Endpoint) - ANCOVA	ITT	TL
14.2.3.1.4	Influenza Symptoms - Overall SSC AUC (Secondary Endpoint) - ANCOVA - Multiple Imputation	ITT	
14.2.3.2	Influenza Symptoms - Local SSC AUC (Exploratory Endpoint)	ITT	
14.2.3.3	Influenza Symptoms - General SSC AUC (Exploratory Endpoint)	ITT	
14.2.3.4	Influenza Symptoms - Time to Start of Symptoms (Exploratory Endpoint)	ITT	
14.2.3.5	Influenza Symptoms - Peak Symptoms (Exploratory Endpoint)	ITT	
14.2.3.6	Influenza Symptoms - Time to Peak of Symptoms (Exploratory Endpoint)	ITT	
14.2.3.7	Influenza Symptoms - Time to Cessation of Symptoms (Exploratory Endpoint)	ITT	
14.2.3.8	Influenza Symptoms - Duration of Symptoms (Exploratory Endpoint)	ITT	
14.2.3.9	Influenza Symptoms - Overall SSC Score Actual Values Over Time	ITT	
14.2.3.10	Influenza Symptoms - Overall SSC Score Changes Over Time	ITT	
14.2.3.11	Influenza Symptoms - Overall SSC Score Changes Mixed Model for Repeated Measures	ITT	
14.2.3.12	Influenza Symptoms - Local SSC Score Actual Values Over Time	ITT	
14.2.3.13	Influenza Symptoms - Local SSC Score Changes Over Time	ITT	
14.2.3.14	Influenza Symptoms - General SSC Score Actual Values Over Time	ITT	
14.2.3.15	Influenza Symptoms - General SSC Score Changes Over Time	ITT	
14.2.3.16	Influenza Symptoms - Total Number of Days of Fever (Exploratory Endpoint)	ITT	
14.2.3.17	Influenza Symptoms - Total Mucus Production (Exploratory Endpoint)	ITT	
14.2.3.18	Influenza Symptoms - Time to Feeling Well Enough to Go to Work	ITT	
IMMUNOGENICITY			
14.2.4.1	T Cell Response Actual Values Over Time (ELISpot Results)	ITT	
14.2.4.2	T Cell Response Changes Over Time (ELISpot Results)	ITT	

	Statistical Analysis Plan	
FLU010	Final analysis	Final 3.0 of 15JUN2020

14.2.4.3 T Cell Response Status (ELISpot Results) ITT
14.2.4.4 Antibody Response Actual Values Over Time ITT
14.2.4.5 Antibody Response Changes Over Time ITT

SAFETY

ADVERSE EVENTS

14.3.1.1 Adverse Events and Solicited Symptoms Overview SAF
14.3.1.2 Treatment-Emergent Adverse Events by MedDRA System Organ Class and Preferred Term SAF
14.3.1.3 Treatment-Emergent Adverse Events of Special Interest by MedDRA System Organ Class and Preferred Term SAF
14.3.1.4 Serious Treatment-Emergent Adverse Events by MedDRA System Organ Class and Preferred Term SAF
14.3.1.5 Non-serious Treatment-Emergent Adverse Events by MedDRA System Organ Class and Preferred Term SAF
14.3.1.6 Grade 3 or More Treatment-Emergent Adverse Events by MedDRA System Organ Class and Preferred Term SAF
14.3.1.7 Treatment Related Treatment-Emergent Adverse Events by MedDRA System Organ Class and Preferred Term SAF
14.3.1.8 Serious Treatment Related Treatment-Emergent Adverse Events by MedDRA System Organ Class and Preferred Term SAF
14.3.1.9 Treatment-Emergent Adverse Events Resulting in Study Discontinuation by MedDRA System Organ Class and Preferred Term SAF
14.3.1.10 Treatment-Emergent Adverse Events by MedDRA System Organ Class, Preferred Term and Maximal Severity SAF
14.3.1.11 Solicited Symptoms SAF
14.3.1.12 Grade 3 or Higher Solicited Symptoms SAF
14.3.1.13 Solicited Symptoms by Maximal Severity SAF

LABORATORY DATA

14.3.2.1 Descriptive Statistics of Laboratory Test Actual Values SAF
14.3.2.2 Descriptive Statistics of Changes From Baseline in Laboratory Test Results SAF
14.3.2.3 Cross-Tabulation of Laboratory Toxicity Grades Versus Baseline SAF
14.3.2.4 Cross-Tabulation of Laboratory Abnormalities Versus Baseline SAF

VITAL SIGNS

14.3.3.1 Descriptive Statistics of Vital Signs Actual Values SAF
14.3.3.2 Descriptive Statistics of Changes From Baseline in Vital Signs SAF
14.3.3.3 Cross-Tabulation of Vital Signs Abnormalities Versus Baseline SAF

ECG

14.3.4.1 Descriptive Statistics of ECG Actual Values SAF
14.3.4.2 Descriptive Statistics of Changes From Baseline in ECG SAF
14.3.4.3 Cross-Tabulation of ECG Abnormalities Versus Baseline SAF
14.3.4.4 Tabulation of QTc Change Abnormalities SAF

	Statistical Analysis Plan	
FLU010	Final analysis	Final 3.0 of 15JUN2020

LUNG FUNCTION

14.3.5.1	Descriptive Statistics of Lung Function Actual Values	SAF
14.3.5.2	Descriptive Statistics of Changes From Baseline in Lung Function	SAF

8.2 LISTINGS

GENERAL CHARACTERISTICS

16.2.1.1	Allocation	RND
16.2.1.2	Code Breaking Information	RND
16.2.1.3	Analysis Phases	SAF
16.2.1.4	Study Discontinuation	SAF
16.2.2.1	Major Protocol Deviations	SAF
16.2.2.2	Violations on Eligibility Criteria	SAF
16.2.2.3	Subjects Randomised but not Treated	RND minus SAF
16.2.4.1	Demographic Data	SAF
16.2.4.2	Tobacco History	SAF
16.2.4.3	Screening Tests	SAF
16.2.4.4	Pregnancy Tests	SAF
16.2.4.5	Medical History	SAF
16.2.4.6	Concomitant Diseases	SAF
16.2.4.7	Prior and Concomitant Therapies	SAF
16.2.4.8	Comments	SAF
16.2.5.1	Vaccination	SAF
16.2.5.2	Challenge	SAF

EFFICACY

16.2.6.1	qPCR Viral Shedding	ITT
16.2.6.2	Culture Viral Shedding	ITT
16.2.6.3	Influenza Symptom Score Card	ITT
16.2.6.4	Fever and Mucus Production	ITT

IMMUNOGENICITY

16.2.6.5	T Cell Response (ELISpot Results)	ITT
16.2.6.6	Antibody Response	ITT

SAFETY

ADVERSE EVENTS

16.2.7.1	Adverse Events	SAF
16.2.7.2	Serious Adverse Events	SAF
16.2.7.3	Fatal Adverse Events	SAF
16.2.7.4	Treatment Emergent Adverse Events Resulting in Study Discontinuation	SAF

	Statistical Analysis Plan	
	FLU010	Final analysis

16.2.7.5 Adverse Events: Coding Information SAF
 16.2.7.6 Physical Examinations Abnormalities SAF

LABORATORY DATA

16.2.8.1 Laboratory Test Results for Subjects with Abnormal Values SAF

VITAL SIGNS

16.2.9.1 Vital Signs Results for Subjects with Abnormal Values SAF

ECG

16.2.10.1 ECG Results for Subjects with Abnormal Values SAF

16.2.10.2 ECG Interpretation and Morphology for Subjects with any Abnormal Interpretation SAF

LUNG FUNCTION

16.2.11.1 Lung Function Results SAF

8.3 FIGURES

EFFICACY

14.2.1.1.1 Log qPCR Mean Actual Values vs. Time Profiles ITT TL
 14.2.1.1.2 Log qPCR Mean Actual Values vs. Time Profiles - Challenge Safety Set CSAF TL
 14.2.1.1.3 Log qPCR Mean Adjusted Actual Values vs. Time Profiles ITT TL
 14.2.1.2 Kaplan-Meier Plot of Time to Start of Viral Shedding (qPCR) ITT TL
 14.2.1.3 Kaplan-Meier Plot of Time to Peak of Viral Shedding (qPCR) ITT
 14.2.1.4 Kaplan-Meier Plot of Time to Cessation of Viral Shedding (qPCR) ITT
 14.2.2.1 Log Culture Mean Actual Values vs. Time Profiles ITT
 14.2.2.2 Kaplan-Meier Plot of Time to Start of Viral Shedding (Culture) ITT
 14.2.2.3 Kaplan-Meier Plot of Time to Peak of Viral Shedding (Culture) ITT
 14.2.2.4 Kaplan-Meier Plot of Time to Cessation of Viral Shedding (Culture) ITT
 14.2.3.1.1 Overall SSC Score Mean Actual Values vs. Time Profiles ITT TL
 14.2.3.1.2 Overall SSC Score Mean Adjusted Changes vs. Time Profiles ITT TL
 14.2.3.2 Local SSC Score Mean Actual Values vs. Time Profiles ITT
 14.2.3.3 General SSC Score Mean Actual Values vs. Time Profiles ITT
 14.2.3.4 Kaplan-Meier Plot of Time to Start of Symptoms ITT
 14.2.3.5 Kaplan-Meier Plot of Time to Peak of Symptoms ITT
 14.2.3.6 Kaplan-Meier Plot of Time to Cessation of Symptoms ITT
 14.2.3.7 Kaplan-Meier Plot of Time to Feel Well Enough to Go to Work ITT
 14.2.3.8 Log qPCR, Log Culture and Overall SSC Score Mean Actual Values vs. Time Profiles ITT

IMMUNOGENICITY

14.2.4.1 Correlation Plots of T Cell Responses (ELISpot Results) to the Primary Endpoint, Symptom Scores and Influenza Incidence ITT
 14.2.4.2 Median T cell Responses Over Time (ELISpot Results) ITT

	Statistical Analysis Plan	
FLU010	Final analysis	Final 3.0 of 15JUN2020

14.2.4.3 Individual T cell Responses Over Time (ELISpot Results)

ITT

14.2.4.4 Median Antibody Responses Over Time

ITT

LABORATORY DATA

14.3.2.1 Boxplot of Laboratory Test Actual Values and Changes Over Time

SAF

	Statistical Analysis Plan	
FLU010	Final analysis	Final 3.0 of 15JUN2020

9. APPENDICES

9.1 SAS CODE

Mann-Whitney U test

```
proc npar1way data=dataset wilcoxon;  
  var AVAL;  
  class TRTP;  
run;
```

Fisher exact test

```
proc freq data= dataset;  
  table AVAL *TRTP/fisher;  
run;
```

Survival analysis with log rank test

```
proc lifetest data= dataset method=KM;  
  time AVAL * CENSOR(1);  
  strata TRTP / test=logrank;  
run;
```

Zero-inflated Poisson

```
proc hpfmm data=dataset;  
  class TRTP;  
  model AVAL = TRTP / dist=Poisson ;  
  model + / dist=Constant;  
run;
```

T-test with checking model assumptions of homogeneity of variances and normality

```
proc glm data= dataset order=internal;  
  class TRTP;  
  model AVAL = TRTP;  
  output out = norm r = resid;  
  means TRTP / hovtest;  
quit;
```

	Statistical Analysis Plan	
FLU010	Final analysis	Final 3.0 of 15JUN2020

```
ods select testsfornormality;  
proc univariate data=norm normal; var resid; run;
```

ANCOVA model

```
proc mixed data=dataset;  
  class TRTP CHCOHORT SEX;  
  model AVAL = TRTP CHCOHORT VACTIME SEX/solution;  
  lsmeans TRTP / diff=control('Placebo') cl;  
run;
```

Multicollinearity testing

```
proc reg data=dataset;  
  model AVAL = TRTP CHCOHORT VACTIME SEX/selection=none vif;  
run;
```

MMRM model

```
proc mixed data=dataset;  
  class USUBJID ATPTN TRTP CHCOHORT SEX;  
  model LGAVAL= TRTP ATPTN ATPTN*TRTP CHCOHORT VACTIME SEX /  
  ddfm=KR S;  
  repeated ATPTN /subject= USUBJID type=UN;  
  lsmeans ATPTN*TRTP / cl pdiff alpha=0.05;  
run;
```

Note: if covariance structure other than UN (unstructured), then ddfm = BW should be used as option to handle degrees of freedom.

Multiple imputation

```
proc mi data= inputdata NIMPUTE=100 SEED=22087 OUT=mnardata;  
  class TRTP;  
  var LGAVALTP1- LGAVALTP22;  
  fcs reg;  
  mnar model (LGAVALTP1- LGAVALTP22)/modelobs=( TRTP ='Placebo'));  
run;
```

	Statistical Analysis Plan	
FLU010	Final analysis	Final 3.0 of 15JUN2020

Permutation-based Resampling Method

```
%macro vect(len=, place=);  
  %do nn=1 %to &len;  
    %if(&nn ^= &place) %then 0;  
    %if(&nn = &place) %then 1;  
  %end;  
%mend vect;  
  
%macro mymult(data_in=, k=);  
  proc multtest data=&data_in perm n=100000 order=data stepperm out=permresults  
  seed = 1;  
  by usbjid atpt;  
  class well;  
  test mean(count/upper);  
  %do peps = 1 %to &k;  
    contrast "peptide&peps" -1 %vect(len=&k, place=&peps);  
  %end;  
  run;  
%mend mymult;  
  
%mymult(data_in=inputdataset,k=2)  
data respstat;  
  set permresults;  
  if 0 lt perm_p lt 0.05 then RESPSTAT = 1;  
  else if perm_p ge 0.05 then RESPSTAT = 0;  
run;
```

	Statistical Analysis Plan											
	FLU010											Final 3.0 of 15JUN2020

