2. EFFICACY AND IMMUNOGENICITY ANALYSES

2.1 EFFICACY

2.1.1 *Available data*

Nasal swabs for influenza virus are collected twice a day (at least 8 hours apart) from Day 2 to Day 10 following intranasal challenge, which are tested for influenza using quantitative polymerase chain reaction (qPCR) and culture. Culture is only done for positive qPCR samples.

The following symptoms of influenza-related infection will be collected twice a day (except for lymphadenopathy, which will be collected once a day only) from Day 1 to Day 11 of challenge on a symptom score card (SSC):

- Local symptoms:
 - Nose (4): nasal congestion (blocked nose), runny nose, sneezing frequency, sinus pressure/pain or facial pain
 - Throat (2): sore throat, difficulty swallowing
 - Eyes (3): tearful/watery eyes, painful eyes, aversion to light
 - Chest/respiratory (3): dry cough, productive (wet) cough, difficulty breathing/tight chest
- General symptoms:
 - Gastrointestinal (4): nausea, stomach ache, vomiting, diarrhoea
 - Body/systemic (12): dizziness, head congestion, headache, muscle aches, feverish, chills or shivering, lack of appetite, felt cold, sweating, tiredness/weakness, sleeping more than usual, lymphadenopathy
 - The following symptoms will only be questions if at least 2 other symptoms with grade 2 or higher are present: nausea, stomach ache, vomiting, diarrhoea, tiredness/weakness, sleeping more than usual.

Each symptom's severity is graded from 0 (absent) to 3 (grade 3 - severe).

Additionally, the SSC also contains the question whether the subject feels well enough to go to work today (yes/no).

Oral body temperature is assessed daily during confinement as part of the vital signs evaluation. During this same period, tissue collection is planned daily to measure daily mucus production.

	Statistical Analysis Plan	
FLU010	Final analysis	Final 3.0 of 15JUN2020

2.1.2 *Endpoints and derivation rules*

2.1.2.1 *PRIMARY ENDPOINT*

Primary endpoint is the viral area under the curve (vAUC) based on the qPCR values. AUC will be calculated using the linear trapezoidal rule, by summing all individual trapezoids, which will be calculated as follows:

$$AUC_{t_i-t_{i+1}} = 1/2 * (L_i + L_{i+1}) * (t_{i+1} - t_i).$$

Where:

- L_i is the log-transformed viral load concentration at time point t_i .
- All time points (including unscheduled time points) from day 2 to day 10 will be considered.
- AUC will be calculated in hours, using actual datetimes of qPCR assessments.

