5.3 IMPUTATION AND ROUNDING RULES

5.3.1 *Missing values*

As culture is only done for positive qPCR values, missing culture results with a qPCR value 'not detected', will be considered as zero (log10).

	Statistical Analysis Plan	
FLU010	Final analysis	Final 3.0 of 15JUN2020

For the calculation of AUCs, the following rules will be used to impute missing values:

- Intermittent missing values will be interpolated. This is implicitly done when using the linear trapezoidal rule.
- In case of trailing missing values, a triangle will be calculated to estimate the area between the timepoint of the last non missing value and the last scheduled assessment, which will be assumed to have a zero value.
- In case of leading missing values, a triangle will be calculated to estimate the area between the first non missing assessment and the first scheduled assessment, which will be assumed to have a zero value.
- In case of trailing missing values with no assessment datetime, the last scheduled assessment datetime will be imputed with challenge datetime + 10 days + 12 hours (for viral load) or + 11 days (SSC)
- In case of leading missing values with no assessment datetime, the first scheduled assessment datetime will be imputed with challenge datetime – 1 min + 1 day (viral load) or with challenge datetime – 1 min (SSC)

Overall/Local/General SSC score will only be calculated if sufficient signs and symptoms are available for each body system: 3/4 nose; 1/2 throat; 2/3 eyes; 2/3 chest/respiratory; 3/4 gastrointestinal and 8/12 body/systemic. Symptoms that are questioned if at least 2 other symptoms with grade 2 or higher are present should only be considered as missing if the condition is met and no value is available.

In case percentage of missing data exceeds 5% for qPCR viral load or for overall SSC, a sensitivity analysis will be done for the AUC based endpoints by using a placebo-based multiple imputation which assumes that all missing viral load concentrations/signs and symptom scores are missing not at random (MNAR). This approach can be considered conservative as subjects from the active treatment arm would adopt the outcome model estimated from the placebo arm.

For the safety analysis, no imputation will be done of missing values (i.e. observed cases analysis).

5.3.2 *Handling partially or completely missing datetimes in calculations*

Partially missing datetime of event will be imputed as follows for the calculation of AUC:

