- Missing time will be imputed with challenge time - 5 min for morning samples and challenge time + 12 h for evening samples.
- Missing date will be imputed based on the scheduled timepoint: missing date on Day 3 = challenge date + 2 days

Partially missing date of event will be imputed as follows for the calculation of time to start and time to peak of viral shedding:

- Missing time will be imputed with challenge time - 5 min for morning samples and challenge time + 12 h for evening samples.
- Missing day will be imputed with 1
- Missing day and month will be imputed with 01JAN

	Statistical Analysis Plan	
FLU010	Final analysis	Final 3.0 of 15JUN2020

Partially missing date of event will be imputed as follows for the calculation of time to cessation of viral shedding:

- Missing time will be imputed with challenge time - 5 min for morning samples and challenge time + 12 h for evening samples.
- Missing day will be imputed with last day of the month
- Missing day and month will be imputed with 31DEC

Partially missing start and stop dates of events will be imputed as follows for the calculation of duration of viral shedding:

- Missing time will be imputed with challenge time - 5 min for morning samples and challenge time + 12 h for evening samples.
- Missing start day will be imputed with 1
- Missing start day and month will be imputed with 01JAN
- Missing stop day will be imputed with last day of the month
- Missing stop day and month will be imputed with 31DEC

Note: If imputation of the start date results in a start date posterior to the stop date / anterior to challenge, the start date will be imputed with the stop date / challenge date respectively. If imputation of the stop date results in a stop date anterior to the start date / posterior to date of last contact, the stop date will be imputed with the start date / date of last contact respectively.

5.3.3 *Values below or above a threshold*

Safety values expressed as below (or above) the detection limit will be imputed by the value of the detection limit itself. Listings will always show the non-imputed values.

Viral load values reported as $> XX$ will be imputed with XX . Viral load values reported as $< XX$ will be imputed with $XX/\sqrt{2}$. For values reported as 'not detected', the \log_{10} viral load will be imputed with 0.

Immunogenicity values reported as $> XX$ will be imputed with XX . Immunogenicity values reported as $< XX$ will be imputed with $XX/2$.

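### The SAP's multiple-imputation code does not fit the primary vAUC: it lists 22 time points for 18 scheduled swabs and, as a separate fault, draws unbounded normal values for a log viral load floored at 0

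*SAP*

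**What the plan says.** SAP 2.1.1 sets the sampling: "Nasal swabs for influenza virus are collected twice a day (at least 8 hours apart) from Day 2 to Day 10". Section 2.1.2.1 computes the vAUC from log-transformed loads by the linear trapezoidal rule, and section 5.3.4 rounds it to an integer. For a sample in which no virus is detected, section 5.3.3 says that the log10 "viral load will be imputed with 0".

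For the main analysis, section 5.3.1 interpolates intermittent gaps and closes leading and trailing gaps with a triangle to zero. If more than 5% of qPCR or overall symptom-score (SSC) data are missing, "a sensitivity analysis will be done for the AUC based endpoints by using a placebo-based multiple imputation". For vAUC the results go to table 14.2.1.1.4 ("qPCR Viral Shedding - qPCR vAUC (Primary Endpoint) - Multiple Imputation") and to its ANCOVA companion, 14.2.1.1.6.

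Section 9.1 holds one code block for this. Its variable list is "var LGAVALTP1- LGAVALTP22", its method is `fcs reg` with no minimum or other constraint, and its reference-arm statement reads "mnar model (LGAVALTP1- LGAVALTP22)/modelobs=( TRTP ='Placebo" (the brackets do not balance as printed). It requests 100 imputations. No text or code says how the Mann-Whitney result is combined over them.

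**The concern.** The variable list does not match the endpoint that the block is meant to serve. Separately, the imputation model is wrong for this variable. Log10 viral load cannot fall below 0, and participants who do not become infected sit at exactly 0 throughout. A normal regression draw can be negative and almost never equals 0. An all-negative participant with one missing swab has a vAUC of 0 in the primary analysis, but in the sensitivity analysis receives an invented positive or negative area. The planned rank test then separates participants who should be tied, and some of them rank as better than uninfected. They belong to the group that a working vaccine would enlarge. At stake is how clearly a triggered sensitivity analysis can be read, not the primary result.

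**Working it through.** **Count of time points.**
- qPCR: Day 2 to Day 10 is 9 days; 9 x 2 = 18 (SAP 2.1.1).
- SSC, SAP 2.1.1 wording: Day 1 to Day 11 twice a day; 11 x 2 = 22.
- SSC, protocol Time and Events footnote (once only on Day 11): 10 x 2 + 1 = 21. The score card in SAP 9.2 also appears to have a single Day 11 column.

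So the coded 22 is reproduced by the SAP's SSC wording and not by the swab schedule, which it exceeds by 4. The LG prefix, used in the MMRM code for log viral load, points to qPCR. The block carries a viral-load name and a symptom-card count, which marks it as an unadapted template.

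**What one imputed value does.** Take an all-zero series with one imputed value v.
- Interior swab: the two adjacent gaps sum to 24 h, so AUC = ½ x v x 24 = 12v.
- First or last swab at nominal 12 h spacing: AUC = ½ x v x 12 = 6v.
- After rounding to an integer, the interior AUC stays at 0 only if |12v| ≤ 0.5, that is |v| ≤ 0.042. A normal draw seldom lands there. It gives a negative AUC once v falls below that band.
- Under the primary rule v is interpolated between zeros, so AUC = 0.

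**Trigger and reach.** Planned swabs: 134 x 18 = 2,412; 5% is 120.6, so at least 121 must be missing. At 5%, the share of participants with any missing swab runs from about 5% (all missingness in complete dropouts) to 1 - 0.95^18 = 60% (independent scatter).

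**Simulation of the coded method** (80 vs 54 participants, 18 time points, regression fitted on placebo). The documents give no vAUC mean or SD, so curve shapes and missingness patterns are assumptions. Settings B and C give ranges. "Non-zero" and "negative" AUC refer to uninfected participants with a missing swab.

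| Setting | Non-zero AUC | Negative AUC | Effect on comparison |
|---|---|---|---|
| A: 6.4% missing; 58% vs 83% infected | 97% | 46% | mean difference -113.5, against -116.1 with complete data |
| B: attack rate 60-90%; 5-10% missing; integer rounding | 86-95% | 42-49% | z moved by about 0.08 on average (at 83% attack rate, 8% missing) |
| C: scattered missingness or dropout | 95-100% | 33-47% | z moved by 0.07-0.13 |

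Of all imputed values, 29% (A) and 20-33% (B) were below 0. In A the shift is 2.6 / 116.1 = 2.2%, towards the null. In B the false areas had a median size of 4-8 log10-hours (95th percentile 18-32), against about 600 for infected participants.

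**Alternatives.**
- Predictive mean matching gave no negative AUCs. Non-zero AUCs fell to 2% in A, and in C to 0-1% with scattered missingness and 33-40% with dropout. In A the mean difference was -115.9. In C it halved the z error under scattered missingness, but not under dropout.
- Truncation at 0 removes negative areas, but in C it left about 60-100% of these participants non-zero and did not reduce the z error.

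**The case against.** Several points count against making much of this, and most of them stand.

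- *The count does no harm by itself.* A reader might infer that the wrong count produces the false areas. It does not; the unbounded model does. The two faults are independent.
- *22 is not arbitrary.* It matches SAP 2.1.1 for the SSC, and section 5.3.1 applies the imputation to both endpoints. The count is therefore wrong for qPCR and unsettled (21 or 22) for the SSC.
- *The extra four could be unscheduled samples.* Section 2.1.2.1 does say "All time points (including unscheduled time points) from day 2 to day 10 will be considered". But unscheduled samples share no common time across participants, so a fixed numbered list cannot hold them. This does not rescue the count.
- *Section 9.1 is illustrative code.* The SAP's change log calls one of its blocks sample code, and the unbalanced brackets mean that this block must be edited anyway. But no other part of the SAP specifies the imputation model, so the block is the plan.
- *Other analyses address missing data.* A reader might infer that this is the only such check. The SAP does not support that. Section 5.1.1 repeats the primary analysis in the per-protocol set, which drops participants who leave quarantine early, if that set differs from ITT. Section 2.1.3 adds an MMRM on log viral load, which does not use the zero-anchored triangles. What remains true is that the imputation is the only planned vAUC analysis that changes the missing-data assumption in the full ITT set.
- *The numerical effect is small.* This stands. The shift in A is also towards the null, in line with the SAP's description of the approach as conservative.

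**Conclusion.** The imputation code is wrong for the primary vAUC in two unrelated ways: 22 variables for 18 scheduled swabs, and unbounded normal draws for a variable with a floor and a point mass at 0. If triggered and run as coded, nearly all uninfected participants with a missing swab would receive a non-zero AUC, and roughly a third to a half a negative one.

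The consequence is limited. For vAUC it is confined to two sensitivity tables and depends on more than 5% missing. It shifts the Mann-Whitney z by about 0.1 and the mean difference by about 2%. A stronger reading, that the primary result is biased or its robustness cannot be assessed, is not supported: the primary test does not use this code, and the false areas are small beside those of infected participants. The direction of the fault follows from the arithmetic. The percentages and z shifts rest on assumed curves, attack rates and missingness. The absent pooling rule is missing detail to settle in the same edit. The change is worth making because the stated method can return impossible values and the remedy is cheap.

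**What to change.** In SAP 5.3.1 and 9.1:

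1. Write one imputation call per endpoint. Use `LGAVALTP1-LGAVALTP18` for qPCR. For the SSC, first reconcile 21 (protocol footnote and score card) with 22 (SAP 2.1.1), then list that number under its own variable name. State how unscheduled swabs enter the imputed vAUC.
2. Replace `fcs reg` with predictive mean matching from placebo donors (`fcs regpmm`). Truncation at 0 alone is not enough, because it leaves most of the affected participants non-zero.
3. State how the rank comparison is pooled over the 100 imputations, for example by applying Rubin's rules to the rank effect size and its variance. Correct the brackets in the reference-arm statement.

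The cost is a few lines of SAP text and code, with no change to data collection or to the primary analysis. The downside is that with at most 54 placebo donors, matching may slightly understate the variance between imputations. It also brought no gain in z accuracy when the missingness was dropout.
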